14.3.5 Other Effect Measures

14.3.5.1 Performance Status

Participants will be graded according to ECOG score.

14.3.5.2 Overall survival time

From date of first dose (date of first post-surgery treatment for participants in group 2) to date of death due to any cause.

14.3.5.3 Progression-free survival time

From date of first dose (date of first post-surgery treatment for participants in group 2) to date of progression or death. Participants who stop treatment for causes other than progression may be censored if other therapy is initiated or if regular assessments for assessing progression are no longer available.

RANO	Response Assessment in Neuro-Oncology

1 Introduction

This statistical analysis plan (SAP) describes all planned analyses for the Clinical Study Report (CSR) of study CBGJ398X2201, a multi-center, open label, phase II study of BGJ398 for the treatment of patients with recurrent GBM and/or other glioma subtypes, whose tumors harbor FGFR1-TACC1, FGFR3-TACC3 fusion and/or activating mutation in FGFR1, FGFR2, or FGFR3 gene.

[figure not shown]
The content of this SAP is based on protocol CBGJ398X2201 Amendment version 2. All decisions regarding final analysis, as defined in the SAP document, have been made prior to database lock of the study data. Detailed tables, figures and listings can be found in TFL shells version 1.0.

1.1 Study design

The study is planned to enroll patients with recurrent GBM in two groups. Non Surgery Group enrolls patients who are not candidates for surgery. Patients in Non Surgery Group receive BGJ398 on a three weeks on, one week off schedule. Surgery Group enrolls patients who are surgical candidates. Patients in Surgery Group receive BGJ398 for 5-10 days prior to surgery. After recovery of surgery (a minimum of two weeks and no more than six weeks following surgery), patients in Surgery Group receive BGJ398 on a three weeks on, one week off schedule. Patients from both Non Surgery Group and Surgery Group are evaluated for tumor response and progression by Gd-enhanced MRI every 8 weeks until disease progression/discontinuation from study using RANO criteria.

The study plans to enroll 34 adult patients with histologically confirmed recurrent GBM and/or other glioma subtypes with FGFR1-TACC1, FGFR3-TACC3 fusion and/or activating mutation in FGFR1, 2, or 3.

Figure 1-1 Study design

1.2 Study objectives and endpoints

Objectives and related endpoints are described in Table 1-1 below.

Table 1-1 Objectives and related endpoints

Objective	Endpoint
Primary	
To assess the anti-tumor activity of BGJ398 for patients with GBM and/or other glioma subtypes with FGFR1-TACC1, FGFR3-TACC3 fusion and/or activating mutation in FGFR1,2 or 3, based on PFS6	PFS rate at 6 months as defined by RANO criteria as assessed by the investigator
Secondary	
To further assess the anti-tumor activity of BGJ398 for patients with GBM and/or other glioma subtypes with FGFR1-TACC1, FGFR3-TACC3 fusion and/or activating mutation in FGFR1,2or 3, based on ORR	ORR (patients with measurable disease) as defined by RANO criteria as assessed by the investigator

Objective	Endpoint
To further assess the anti-tumor activity of BGJ398 for patients with GBM and/or other glioma subtypes with FGFR1-TACC1, FGFR3-TACC3 fusion and/or activating mutation with in FGFR1,2or 3, based on OS	Overall survival (OS)
To characterize the safety and tolerability of BGJ398	Safety: type, frequency, and severity of AEs and SAEs; Tolerability: dose interruptions, reductions and dose intensity, and evaluations of laboratory values

2 Statistical methods

2.1 Data analysis general information

The final analysis will be performed by Novartis personnel. SAS[®] version 9.4 will be used to perform all data analyses and to generate tables, figures and listings.

Data included in the analysis

The study data will be analyzed and reported (in a primary CSR if final DBL has not occurred) based on all patient's data when all patients have completed at least 6 cycles of treatment or discontinued the study. The primary CSR will include all outputs planned in the TFL Shells documents. Additional data of any patients continuing to receive BGJ398 beyond the cut-off date, as allowed by the CSP, will be summarized in a final CSR that will be prepared once all patients have discontinued the study or at the end of the study (end of survival follow up period) which is one year after the last patient's last dose of study treatment, whichever occurs first.

General analysis conventions

Pooling of centers: Unless specified otherwise, data from all participating centers will be combined for the analysis, so that an adequate number of patients will be available for analysis. Due to expected small number of patients enrolled at centers, no center effect will be assessed.

Qualitative data (e.g., gender, race, etc.) will be summarized by means of contingency tables, a missing category will be included as applicable. Percentages will be calculated using the number of patients in the relevant population or subgroup as the denominator.

Quantitative data (e.g., age, body weight, etc.) will be summarized by appropriate descriptive statistics (i.e. mean, standard deviation, median, minimum, and maximum).

2.1.1 General definitions

Investigational drug and study treatment

Investigational drug refers to the BGJ398 only.

Study treatment = investigational drug.

Date of first administration of investigational drug

The date of first administration of investigational drug is defined as the first date when a non-zero dose of investigational drug BGJ398 is administered and recorded on the Dosage Administration Record (DAR) (e)CRF. The date of first administration of investigational drug will also be referred as the start date of investigational drug.

Date of last administration of investigational drug

The date of last administration of investigational drug is defined as is the last date when a nonzero dose of investigational drug is administered and recorded on DAR (e)CRF. The date of last administration of investigational drug will also be referred as the last date of investigational drug.

Study day

The study day, describes the day of the event or assessment date, relative to the reference start date.

The study day is defined as:

- The date of the event (visit date, onset date of an event, assessment date etc.) – reference start date + 1 if event is on or after the reference start date;
- The date of the event (visit date, onset date of an event, assessment date etc.) – reference start date if event precedes the reference start date.

The reference date for all assessments (safety, efficacy, ████ etc) is the start date of study treatment.

The study day will be displayed in the data listings. If an event starts before the reference start date, the study day displayed on the listing will be negative.

Time unit

A year length is defined as 365.25 days. A month length is 30.4375 days (365.25/12). If duration is reported in months, duration in days will be divided by 30.4375. If duration is reported in years, duration in days will be divided by 365.25. A week length is 7 days. If duration is reported in weeks, duration in days will be divided by 7.

Baseline

For **non-efficacy assessments**, **Baseline** is the last available and valid assessment performed or value measured within 21 days before the first administration of study treatment, unless otherwise stated under the related assessment section. Baseline can be the day before first treatment administration or the same day as first treatment administration if a pre-dose assessment/value is available (e.g., ECG, [REDACTED]).

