6.1.1 Dosing regimen

Table 6-1 Dose and treatment schedule

Study treatments	Pharmaceutical form and route of administration	Strength	Frequency and/or Regimen
BGJ398	Capsule for oral use	100 mg	Daily, 3 weeks on 1 week off schedule
BGJ398	Capsule for oral use	25 mg	Daily, 3 weeks on 1 week off schedule

Patients should be instructed to take the daily dose of BGJ398 in the morning, at approximately the same time each day (24 ± 2 hrs. interval),

 The investigator should instruct the patient to take the study drug exactly as prescribed to promote compliance. All dosages prescribed and dispensed to the patient and all dose changes during the study must be recorded on the Dosage Administration Record CRF.

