7.1.3 Treatment period

During the treatment period, the patient is obliged to follow the investigators instructions with regards to contraception, concomitant medications and dosing regimen. There is no fixed duration; patients may continue treatment with the study drug until the development of an unacceptable toxicity that precludes any further treatment, disease progression, and /or treatment is discontinued at the discretion of the Investigator or by patient refusal.

For the patients included in group 2 (surgical group), there is a fixed treatment duration of 5 to 10 days before surgery. The last dose should be on the day of surgery, or the day before at the discretion of the investigator. At a minimum of 2 weeks post-surgery, patients may resume study treatment with BGJ398 until experiencing unacceptable toxicity, disease progression and/or the treatment is discontinued at the discretion of the investigator or by patient refusal (withdrawal of consent). Day 1 of treatment following surgery will be considered to be Cycle 1 Day 1. For details of assessments during the treatment period, refer to [Table 7-1](#).

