2.4 Treatments (study treatment, rescue medication, concomitant therapies, compliance)

2.4.1 Study treatment / compliance

Duration of exposure, actual dose intensity (ADI) and relative dose intensity (RDI) will be summarized. The number (%) of subjects who have dose reductions or interruptions, and the reasons, will be summarized.

Subject level listings of all doses administered on treatment along with dose change reasons will be produced.

The safety set will be used for all summaries and listings of study treatment.

Duration of exposure to study treatment

The duration of exposure is calculated as detailed below.

For patients who discontinued permanently from the study as of the data cut-off date:

$$\text{Duration of exposure (days)} = (\text{end date of study drug} + X) - (\text{start date of study drug}) + 1,$$

where study drug is BGJ398 and X is the number of days from last administered dose to the next planned dose taking into account the minimal allowed dosing interval. If the last dose of a cycle was taken later than the scheduled cycle length (28 days), X will be set to 0 days. For BGJ398, X equals to 0 if the cycle day of the last dose is less than 21 days; otherwise, X equals to (28 – cycle day of the last dose).

For patients who are still on-treatment as of data cut-off date:

$$\text{Duration of exposure (days)} = \text{data cut-off date} - (\text{start date of study drug}) + 1.$$

Summary of duration of exposure of study treatment in weeks will include categorical summaries and continuous summaries (i.e. mean, standard deviation etc.). Duration of exposure will be categorized into time intervals (i.e. < 4 weeks, 4 - < 8 weeks, 8 - < 12 weeks, 12 - < 16 weeks, 16 - < 24 weeks, 24 - < 32 weeks and >= 32 weeks); frequency counts and percentages will be presented for the number (%) of subjects in each interval.

Exposure will be summarized on the Safety Set.

Cumulative dose

Cumulative dose of a study treatment is defined as the total dose given during the study treatment exposure and will be summarized for each of the study treatment components.

The **planned cumulative dose** for a study treatment component refers to the total planned dose as per the protocol up to the last date of investigational drug administration.

The planned cumulative dose is not summarized/listed. It is used for relative dose intensity calculations.

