The **actual cumulative dose** refers to the total actual dose administered, over the duration for which the subject is on the study treatment as documented in the DAR (e)CRF.

For patients who did not take any drug the cumulative dose is by definition equal to zero.

Relative dose intensity

Actual dose intensity (ADI) for patients with non-zero duration of exposure is defined as follows:

$$\text{ADI (mg / day)} = \text{Actual Cumulative dose (mg)} / \text{Duration of exposure to study treatment (day)}.$$

For patients who did not take any drug the ADI is by definition equal to zero.

Planned dose intensity (PDI) is defined as follows:

$$\text{PDI (mg / day)} = \text{Planned Cumulative dose (mg)} / \text{Duration of exposure (day)}.$$

Relative dose intensity (RDI) is defined as follows:

$$\text{RDI} = \text{ADI (mg / day)} / \text{PDI (mg / day)}.$$

Dose reductions, interruptions or permanent discontinuations

The number of subjects who have dose reductions, dose interruptions, or dose permanent discontinuations, and the reasons, will be summarized. 'Dose Changed', 'Dose interrupted', and 'Dose permanently discontinued' fields from the DAR (e)CRF will be used to determine the dose reductions, dose interruptions, and permanent discontinuations, respectively. **Note:** planned 1 week off in dosing schedule will not be collected or counted as dose interruption. The corresponding field 'Reason' for dose changed, dose interrupted, and dose permanently discontinued will be used to summarize the reasons.

A dose reduction is defined as a decrease in total daily dose from the protocol planned dose, and a decrease from the previous non-zero dose, even if this decrease has been directly preceded by an interruption, and the dose change flag is checked. For example, in the sequence 125 mg – 0 mg – 100 mg, the 100 mg dose will be counted as a reduction.

A dose interruption is defined as an instance that no study drug (0 mg) is taken when the protocol planned dose is non-zero. For example, in the sequence 125 mg – 0 mg – 100 mg, the 0 mg dose will be counted as an interruption.

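### In operated Surgery Group patients the SAP starts exposure and visit windows at the pre-surgical dose, so the planned surgical pause inflates duration, lowers mg/day dose intensity and shifts visit labels

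*SAP*

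**What the plan says.** **Start date.** SAP 2.1.1: "The date of first administration of investigational drug is defined as the first date when a non-zero dose of investigational drug BGJ398 is administered", as recorded on the Dosage Administration Record. Study treatment means BGJ398 only, and there is no separate rule for the Surgery Group. The reference date for study day, for all assessments, "is the start date of study treatment". Pre-surgical doses are on that record, because protocol 6.1.1 requires it: "All dosages prescribed and dispensed to the patient and all dose changes during the study must be recorded on the Dosage Administration Record CRF".

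**Surgery Group schedule.** SAP 1.1: "Patients in Surgery Group receive BGJ398 for 5-10 days prior to surgery". They resume two to six weeks after the operation. Protocol 7.1.3 then fixes the cycle count: "Day 1 of treatment following surgery will be considered to be Cycle 1 Day 1". SAP 2.5.1 and 2.7.2 use this post-surgical origin for PFS and OS.

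**Exposure and dose intensity.** In SAP 2.4.1, duration runs from the start date to the last dose plus X, counting both ends, where "X is the number of days from last administered dose to the next planned dose". Nothing is subtracted for surgery. Actual dose intensity (ADI) is actual cumulative dose over this duration. Planned dose intensity (PDI) is planned cumulative dose over the same duration. Relative dose intensity (RDI) is ADI/PDI.

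**Visits.** Table 2-1 in SAP 2.1.1 slots assessments by study day, with targets 15, 29, 57, 71 and 85, then every 28 days. End of Treatment is slotted by visit instead.

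**The concern.** For an operated patient who resumes, the SAP runs two clocks. PFS and OS start at the first post-surgical dose. Study day, visit windows and exposure start at the pre-surgical dose. The duration formula even mixes the two, since X depends on cycle day, which restarts after surgery, while the start date does not. Section 2.4.1 says that the planned off-week is not an interruption, but it never mentions the planned surgical pause.

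Two outputs are at stake. Dose intensity is part of the tolerability endpoint in SAP Table 1-1, and its mg/day form would fall because of a pause that the protocol itself schedules. By-visit summaries would also place a pre-dose Cycle 1 Day 1 value, taken after two to six weeks off drug, in a window named for a later on-treatment visit.

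**Working it through.** **The plan's own figures first.** With Day 1 = Cycle 1 Day 1 (C1D1), target day = (cycle - 1) x 28 + cycle day. This gives C1D15 = 15, C2D1 = 29, C3D1 = 57, C3D15 = 71 and C4D1 = 85, exactly as in Table 2-1. The table therefore presumes that Day 1 is C1D1.

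**Inputs.**
- Pre-surgical doses p = 5 to 10 (SAP 1.1), with surgery on day p + 1, that is day 6-11 (protocol Table 7-1).
- Resumption g = 14 to 42 days after surgery (SAP 1.1; protocol 4.1).
- 125 mg daily, 21 days of every 28.
- Assumed: full adherence and last dose on cycle day 21, so X = 28 - 21 = 7.

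**Formulas.** C1D1 falls on study day p + 1 + g. After n cycles:
- duration = (p + g) + 28n
- actual cumulative dose = 125 x (p + 21n)
- ADI = actual cumulative dose / duration

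For Group 1, ADI = 125 x 21/28 = 93.75 mg/day.

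**Position of C1D1.** Earliest: 5 + 1 + 14 = day 20. Latest: 10 + 1 + 42 = day 53. If the last pre-surgical dose is taken on the day of surgery, the earliest is one day sooner.

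**Duration and ADI.** The lowest ADI pairs the fewest pre-surgical doses with the longest pause. The highest pairs the most doses with the shortest pause.

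| Cycles | Duration, days | Lowest ADI (p = 5, g = 42) | Highest ADI (p = 10, g = 14) | Share of 93.75 |
|---|---|---|---|---|
| 1 | 47-80 | 3250/75 = 43.3 | 3875/52 = 74.5 | 46-79% |
| 3 | 103-136 | 8500/131 = 64.9 | 9125/108 = 84.5 | 69-90% |
| 6 | 187-220 | 16375/215 = 76.2 | 17000/192 = 88.5 | 81-94% |

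Without the pause, six cycles plus the lead-in last 5 + 168 = 173 to 10 + 168 = 178 days.

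**RDI.** Duration cancels, so RDI = actual / planned cumulative dose. The protocol plans no dose in the pause, so a fully adherent patient has RDI = 1.00. The pause is not an interruption either, because SAP 2.4.1 counts one only when the planned dose is non-zero. RDI would fall (0.48-0.82 after one cycle, 0.82-0.95 after six) only if a programmer ran the 3-on/1-off plan straight through the pause. The SAP text does not support that reading, but does not expressly exclude it.

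**Visit labels.** Applying the Table 2-1 windows (C1D15: 2-21; C2D1: 22-42; C3D1: 43-63; C3D15: 64-77; C4D1: 78-98; from cycle 5, target day - 14 to + 13):

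| True visit | C1D1 on day 20 | C1D1 on day 53 |
|---|---|---|
| C1D1 | day 20: C1D15 | day 53: C3D1 |
| C1D15 | day 34: C2D1 | day 67: C3D15 |
| C2D1 | day 48: C3D1 | day 81: C4D1 |
| C3D1 | day 76: C3D15 | day 109: C5D1 |
| C4D1 | day 104: C5D1 | day 137: C6D1 |

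For any shift of 14 days or more, no visit slotted by study day keeps its own label. From cycle 4 on, Day 1 visits are labelled one or two cycles late.

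**Number of patients.** At the expected 2:1 ratio (protocol 4.1), Group 2 is about 34/3, or 11 patients, if all have surgery and resume.

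**The case against.** The strongest reply is that first-to-last-dose exposure is an ordinary convention. It already includes off-drug time in Group 1 (the off-week through X, and any interruptions), and it matches the on-treatment period used for adverse events. Cutting out the pause alone would not equalise the groups either. After one cycle it gives 3250/33 = 98.5 to 3875/38 = 102.0 mg/day, above 93.75, because the lead-in has no off-week. This stands as an argument against simply excising the pause. It does not justify counting a scheduled surgical break as exposure in a mg/day measure.

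A reader might infer that adherent operated patients would be reported as under-dosed, or that tolerability could not be compared across groups. The documents do not support this. RDI stays at 1.00, no interruption or reduction is recorded, and protocol 10.5.3.5 sets its tolerability categories on RDI. PDI falls by the same proportion as ADI.

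A reader might also infer that published over-time tables will be wrong. SAP 2.1.1 does intend windowed summaries of ECOG status and vital signs. The output sections (2.8.2 to 2.8.4.2), however, describe only worst-value shifts, counts of notable values and listings. Whether a by-visit table exists depends on the TFL shells, which are not part of these documents.

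Finally, the group may be small. SAP 2.2 provides for an empty Surgery Group and names the two groups separately. Separate labels allow separate display, but leave the Surgery Group's own duration, ADI and visit labels as computed above.

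**Conclusion.** The inconsistency is real and minor. In operated patients who resume, the stated rules add 14-42 days of planned pause to exposure and lower ADI at full adherence to 46-79% of the Group 1 value after one cycle, 69-90% after three and 81-94% after six. They also mislabel every visit slotted by study day; End of Treatment is exempt. These figures assume the planned schedule, full 125 mg adherence and a last dose on cycle day 21.

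The effect is confined to descriptive duration, ADI, study-day values in listings and any by-visit summary. PFS6, OS, ORR, treatment-emergent adverse events and worst-value laboratory shifts do not move. RDI, interruptions and reductions do not move provided that planned dose in the pause is zero. The 11 of 34 is a planning figure and not an upper bound; the true number could be none.

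**What to change.** In SAP 2.1.1 and 2.4.1, for Surgery Group patients who are operated on and resume BGJ398:

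- (a) Summarise pre-surgical days and dose separately.
- (b) Compute duration of exposure and ADI from Cycle 1 Day 1 to last dose + X, with only post-surgical doses in the numerator. At full adherence this returns 125 x 21/28 = 93.75 mg/day, the Group 1 value.
- (c) Count the Table 2-1 windows from Cycle 1 Day 1, with a separate pre-surgical/surgery slot.
- (d) State that planned cumulative dose in the surgical pause is zero.

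Keep the first-ever dose as the reference for treatment-emergent adverse events and for the pre-dose baseline.

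The cost is SAP wording and minor programming, with no new data and no change to treatment. The one drawback is that exposure and the adverse-event on-treatment period then have different origins in this group, so each table needs a label saying which it uses.

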In order to summarize ECOG performance status, ████ vital signs, and other data collected over time (including unscheduled visits), the assessments will be time slotted. The following general rule will be applied in creating the assessment windows: If more than one assessment is done within the same time window, the assessment performed closest to the target date will be used. If 2 assessments within a time window are equidistant from the target date, then the earlier of the 2 assessments will be used. If multiple assessments on the same date then the worst case will be used. Data from all assessments (scheduled and unscheduled), including multiple assessments, will be listed.

Table 2-1 Time windows for assessments

Assessment	Target day of assessment	Time Interval
Baseline		≤ Day 1
Cycle 1 Day 15	15	Day 2 to day 21
Cycle 2 Day 1	29	Day 22 to day 42
Cycle 3 Day 1	57	Day 43 to day 63
Cycle 3 Day 15	71	Day 64 to day 77
Cycle 4 Day 1	85	Day 78 to day 98
Cycle k Day 1 (k≥5)	$d=(k-1)*28+1$	Day d-14 to day d+13
End of Treatment		Assessment taken at the end of treatment visit

Last contact date

The last contact date will be derived for patients not known to have died at the analysis cut-off using the last complete date among the following:

Table 2-2 Last contact date data sources

Source data	Conditions
Last contact date/last date patient was known to be alive from Survival Follow-up page	- Patient status is reported to be alive, lost to follow-up or unknown.
Start/End dates from further antineoplastic therapy	Non-missing medication/procedure term.

Source data	Conditions
Start/End dates from drug administration record	Non-missing dose. Doses of 0 are allowed.
End of treatment date from end of treatment page	No condition.
RANO assessment date	Evaluation is marked as 'done'.
Laboratory ████ collection dates	Sample collection marked as 'done'.
Vital signs date	At least one non-missing parameter value
Performance Status date	Non-missing performance status
Start/End dates of AE	Non-missing verbatim term

The last contact date is defined as the latest complete date from the above list on or before the data cut-off date. The cut-off date will not be used for last contact date, unless the patient was seen or contacted on that date. No date post cut-off date will be used. Completely imputed dates (e.g. the analysis cut-off date programmatically imputed to replace the missing end date of a dose administration record) will not be used to derive the last contact date. Partial date imputation is allowed for event (death)/censoring is coming from 'Survival information' (e)CRF.

The last contact date will be used for censoring of patients in the analysis of overall survival.

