7.1 Study flow and visit schedule

For all visits, there is a \pm 3-day window on assessments to take into account scheduling over public or religious holidays, **if not explicitly specified otherwise.** [REDACTED]

[REDACTED] For imaging assessments, a \pm 7 day window is allowed, except for the first post baseline assessment and for confirmatory scans (+7 day window only permitted). All screening assessments, including baseline imaging assessments, must be completed within 28 days before the first dose, with the exception of the serum pregnancy test (β -hCG) that needs to be performed \leq 72hrs before the first dose of study treatment. Every effort must be made to follow the schedule outlined in [Table 7-1](#).

[Table 7-1](#) lists all of the assessments and indicates with an “X”, the visits when they are performed. The table indicates which assessments produce data to be entered into the database (D) or remain in source documents only (S) (“Category” column).

Molecular pre-screening assessments can be performed any time prior to the initiation of screening.

Assessments which are indicated to be performed at screening and on Cycle 1 Day 1, need only to be repeated at Cycle 1 Day 1 if screening assessment was more than 3 days earlier.

[figure not shown]
All assessments should be performed as outlined in [Table 7-1](#) and as clinically indicated.

	Category	Reference to section	Molecular pre - screening	Screening	Pre-Surgical Treatment	Day of Surgery	Cycle 1					Cycle 2				Cycle 3	Subsequent cycles	End of study treatment	30 day Follow up	Disease Progression	Survival follow up			
			Screening Phase		Surgical phase (Group 2)			Treatment Phase													Follow-up			
Day of cycle				-28 to -1	1	5-10	6-11	1	2	8	15	22	1	8	15	22	1	22	1	22				
Relevant medical history/current medical conditions	D	7.1.2.3		X																				
Diagnosis and extent of cancer	D	7.1.2.3		X																				
Prior antineoplastic therapy	D	7.1.2.3		X																				
Prior/ concomitant medications	D	6.3		X	X	X	X	Continuous													X	X		
Antineoplastic therapies since discontinuation of study treatment	D	7.1.4																			X	X	X	X
Physical examination	S	7.2.2.1		X				X		X		X	X	X		X	X	X	X	X	X			
Height	D	7.2.2.3		X																				
Weight	D	7.2.2.3		X				X					X				X				X			
Vital signs	D	7.2.2.2		X				X		X	X	X	X	X	X	X	X	X	X	X	X			
Performance status	D	7.2.2.4		X				X				X	X			X	X		X		X			
Hematology	D	7.2.2.5.1		X				X					X				X		X		X			

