10.5.3.4 Other safety data

Data from other tests (e.g., electrocardiogram or vital signs) will be listed, notable values will be flagged, and any other information collected will be listed as appropriate. Any statistical tests performed to explore the data will be used only to highlight any interesting comparisons that may warrant further consideration. Additionally, the following outputs will be produced:

ECG

- shift table baseline to worst on-treatment result for overall assessments
- listing of ECG evaluations for all patients with at least one abnormality.

Vital signs

[figure not shown]
- shift table baseline to worst on-treatment result
- table with descriptive statistics at baseline, one or several post-baseline time points and change from baseline to this/these post-baseline time points.

[figure not shown]
Ocular

[figure not shown]
- Table with frequency of ocular events by cycle will be produced by treatment group.
- Listing of ocular assessments for all patients with at least one abnormality.

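### SAP Table 2-1 does not match the visit schedule: it has a Cycle 3 Day 15 window that no scheduled visit fills, no Day 22 window, and a day count that misplaces post-surgical cycles

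*SAP*

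**What the plan says.** **Windows.** SAP 2.1.1 introduces its windows with "In order to summarize ECOG performance status", then a redacted item, then "vital signs, and other data collected over time (including unscheduled visits), the assessments will be time slotted". Table 2-1 sets targets at days 15, 29, 57, 71 and 85, then Day 1 of each cycle from Cycle 5 on. The window labelled Cycle 2 Day 1 is "Day 22 to day 42"; the one labelled Cycle 3 Day 15 is "Day 64 to day 77". Within a window, "If more than one assessment is done within the same time window, the assessment performed closest to the target date will be used", and a tie goes to the earlier assessment. Study day is counted from the start of study treatment.

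**Schedule.** Protocol 7.1 says "Every effort must be made to follow the schedule outlined in" Table 7-1. That table has visit columns for Days 1, 2, 8, 15 and 22 in Cycle 1, Days 1, 8, 15 and 22 in Cycle 2, and Days 1 and 22 in Cycle 3 and later. Visits may move by 3 days either way. Dosing is on Days 1 to 21 of 28 (Protocol 2.2), and vital signs are taken before dosing (Protocol 7.2.2.2).

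**Outputs.** SAP 2.8.2 builds laboratory shift tables on the worst on-treatment value and says that all available assessments are used. SAP 2.8.4.1 and 2.8.4.2 count patients with notable ECG and vital-sign values without saying whether windows apply. SAP 2.8.3 lists ECOG frequencies and gives no visit structure.

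**Ocular data.** Protocol 10.5.3.4 plans this output: "Table with frequency of ocular events by cycle will be produced by treatment group". It also plans a listing of ocular assessments for patients with any abnormality. The readable SAP 2.8.4 covers ECG and vital signs only. SAP section 4 declares one change, the interim analysis that was not done.

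**The concern.** A window table should give each scheduled visit that is to be summarised its own slot. Table 2-1 instead folds Day 22 into the next cycle's Day 1 window, where it is 7 days off target and loses to Day 1. Under a three-weeks-on, one-week-off schedule this matters. Day 22 comes straight after 21 days of dosing, whereas a pre-dose Day 1 value follows 7 planned days without drug. A by-time-point summary on these windows would mostly describe patients after recovery time.

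The empty window can also mislabel data. A Cycle 3 Day 22 visit made 1 to 3 days early falls on days 75 to 77 and would be shown as Cycle 3 Day 15.

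Operated patients restart at Cycle 1 Day 1 after surgery, but their study day runs from the pre-surgical dose. Window labels and actual cycles then disagree.

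The ocular outputs are a separate matter of traceability: the protocol plans them, and the readable SAP neither repeats nor withdraws them.

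**Working it through.** **Inputs.** Visit days come from Protocol Table 7-1; windows and selection rule from SAP 2.1.1. Study day = (cycle − 1) × 28 + cycle day. The first check assumes the Non Surgery Group, visits on time and no dose delays.

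**Reproducing the SAP targets.** Cycle 1 Day 15 = 15; Cycle 2 Day 1 = 28 + 1 = 29; Cycle 3 Day 1 = 56 + 1 = 57; Cycle 3 Day 15 = 56 + 15 = 71; Cycle 4 Day 1 = 84 + 1 = 85; Cycle 5 Day 1 = 112 + 1 = 113. All agree with Table 2-1, and the windows are contiguous.

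**Vital signs through Cycle 5 Day 1.** The 12 scheduled post-baseline days are 8, 15, 22, 29, 36, 43, 50, 57, 78, 85, 106 and 113.

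| Window label | Days | Scheduled visits inside | Kept | Displaced |
|---|---|---|---|---|
| Cycle 1 Day 15 | 2–21 | 8, 15 | 15 | 8 |
| Cycle 2 Day 1 | 22–42 | 22, 29, 36 | 29 | 22, 36 |
| Cycle 3 Day 1 | 43–63 | 43, 50, 57 | 57 | 43, 50 |
| Cycle 3 Day 15 | 64–77 | none | none | none |
| Cycle 4 Day 1 | 78–98 | 78, 85 | 85 | 78 |
| Cycle 5 Day 1 | 99–126 | 106, 113 | 113 | 106 |

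Kept: 5 of 12, of which four are Day 1 and one (day 15) falls in a dosing block. Displaced: 7, of which four are Day 22 visits (22, 50, 78, 106) and three fall in dosing blocks (8, 36, 43). Carried on to Cycle 7 Day 1, 7 of 8 windows fill: six with Day 1 values, one with a mid-dosing value, and none of the six Day 22 visits.

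**ECOG.** Post-baseline assessments are on Day 22 of Cycles 1 and 2 and Day 1 of each cycle from Cycle 2. To Cycle 7 Day 1, six windows fill, all with Day 1. Days 22 and 50 lose to days 29 and 57.

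**Measures not displaced.** Post-baseline hematology and ECG are scheduled on Day 1 only, and eye examinations on Cycle 1 Day 15 and Day 1 only. Day 22 windows would change nothing for their scheduled visits.

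**Surgery Group, operated patients.** Pre-surgical dosing lasts 5 to 10 days and recovery 2 to 6 weeks. Post-surgical Cycle 1 Day 1 is therefore shifted by about 5 + 14 = 19 to 10 + 42 = 52 days. Take a shift of 7 + 28 = 35 days as an example. Cycle 1 Day 22 falls on 22 + 35 = 57, the Cycle 3 Day 1 target. Cycle 2 Day 22 falls on 50 + 35 = 85, the Cycle 4 Day 1 target. Here the labelled Day 1 rows would hold Day 22 values.

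**Effect of alignment.** Giving each scheduled vital-sign visit its own window, with midpoint boundaries, fills all 16 windows to Cycle 7 Day 1: six at Day 22, four mid-dosing and six at Day 1.

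**The case against.** The strongest reply is that the readable SAP names no by-visit safety table. Laboratory tables use the worst value from all assessments, ECG and vital-sign tables count notable values, and every assessment is listed. A reader might infer from Table 2-1 that the safety tables as a whole would show almost only off-drug values. The documents do not support that. What remains is that SAP 2.1.1 says the slotting is done to summarise ECOG and vital signs, and that SAP 2.8.4, unlike 2.8.2, does not say its counts use all assessments. Read literally, the rule could limit those counts to one value per window.

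A reader might also call Day 22 an on-drug day. Dosing runs on Days 1 to 21, so Day 22 is the first planned off-drug day. Its value is that it reflects the end of the dosing block. No hidden safety signal is shown.

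Protocol 10.5.3.4 asks for vital-sign statistics at one or several post-baseline time points, so weekly rows are not required. That stands: the sponsor may choose which visits to show. It does not justify a row for an unscheduled visit or windows that merge separate visits. An empty window does no harm in itself and may catch unscheduled visits; the risk is a mislabelled early Day 22 visit.

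On ocular data, a reader might infer that the outputs were dropped and that eye findings would surface only as adverse events. Neither is established. SAP 2.8 says all safety assessments will be listed, and eye examinations are a protocol safety assessment. SAP 2.9 and 2.10 and the table shells are not in the supplied text, so the by-cycle table may be there.

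**Conclusion.** The mismatch is confirmed, and its reach is limited. In the Non Surgery Group, with visits on time, a windowed vital-sign summary keeps 5 of 12 visits through Cycle 5 Day 1, four of them Day 1 after the week off. It drops every Day 22 value and the Cycle 2 mid-dosing values. Windowed ECOG keeps no Day 22 assessment when Day 1 is available. For operated Surgery Group patients the windows do not track the post-surgical cycles, and the direction of the error depends on the length of the gap. Protocol 4.1 expects about a third of patients in that group; SAP 2.2 allows that it may be empty.

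Efficacy results, adverse-event tables, laboratory worst-value tables and listings do not change. Whether the notable-value counts change depends on a rule that the SAP leaves unstated. The ocular omission is an open question until the unredacted SAP and the shells are checked. The point is worth correcting, but it does not threaten the trial's conclusions.

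**What to change.** 1. Align Table 2-1 with Protocol Table 7-1: remove Cycle 3 Day 15 and add Day 22 windows. One workable set with midpoint boundaries, for visits each given their own row, is: days 2–11 (target 8), 12–18 (15), 19–25 (22), 26–32 (29), 33–39 (36), 40–46 (43), 47–53 (50), 54–67 (57), 68–81 (78), 82–95 (85), and so on for Day 22 and Day 1 of later cycles.
2. For Surgery Group patients who have surgery, count windows from post-surgical Cycle 1 Day 1. Those who do not have surgery keep the first dose as reference.
3. State that the notable vital-sign and ECG counts use all on-treatment assessments, and that windows apply only to by-time-point summaries. Name those summaries.
4. Check the unredacted SAP and the table shells for the ocular-events-by-cycle table and the ocular abnormality listing. If they are absent, restore them in SAP 2.8.4 or declare their removal in section 4.

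The cost is a SAP edit and matching programming. If the ocular outputs are missing, it adds one table and one listing. Table 7-1 marks the vital-sign, ECOG, ECG and eye-examination data for entry in the database, so no new collection is needed.
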